## 2. AIMS/OBJECTIVES

- **2.1 Primary Aim.** Obtain efficacy estimates of daily TENS on CIPN (European Organisation for Research and Treatment of Cancer-CIPN20 (EORTC-CIPN20)) to inform the design of a phase III confirmatory trial.
- **2.2 Secondary Aim 1.** Obtain efficacy estimates of TENS on individual CIPN symptoms (i.e., hot/burning pain, sharp/shooting pain, tingling, numbness, cramping (measured daily via 0 10 Numeric Rating Scale (NRS)).
- **2.3 Secondary Aim 2.** Evaluate the feasibility of conducting, within the URCC NCORP network, a multisite, modified double-blind RCT of TENS for CIPN with physiologic assessments of descending inhibition (i.e., conditioned pain modulation (CPM) test) by assessing the proportions of (a) screened patients who enroll, (b) randomized participants who adhere to the treatment and complete the primary assessment, and (c) randomized participants who complete the CPM test.
- **2.4 Exploratory Aim 1** Investigate the potential effects of TENS on balance, physical function, descending inhibition, lower limb sensation, and anxiety and depression.
- **2.5 Exploratory Aim 2** Establish data to support the construct validity of the Treatment-Induced Neuropathy Assessment Scale (TNAS) and CIPN symptom inventory daily diary by comparison to the EORTC-CIPN20, which is the most commonly used measure of CIPN.

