## 5.3 Schedule of study procedures

# 5.3.1 Screening / Consent Visit (Day -7; -2/+3 days) (approximately 1 hour)

Eligible participants who provide informed consent will be registered and given the daily diary of CIPN symptoms and rescue pain medication consumption, and trained on how to complete it at home during the Baseline Week (i.e., between the Screening and Baseline Visits). They will complete the CPM test and lower limb sensation test. Chemotherapy treatment notes will be collected for all consented participants.

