## 5.3.3 Baseline Visit (Day 0) (approximately 1 hour)

All participants will be randomized according to procedures in **Section 5.3.4** after they arrive for the baseline visit. They will complete the PROs, balance tests, CPM test, and lower limb sensation test. At this time the participants will be given the TENS device (see **Section 5.2** for details of the device) and sufficient electrodes for 6 weeks of the study. They will be trained on how to use the TENS device. Using a standardized script to limit variation in expectations, the unblinded coordinator will lead all participants through the calibration process to identify their ideal intensity setting. The unblinded coordinator will train the participants on how to use the device at home. The unblinded coordinator will also download the Quell Health Account App to the participant's smartphone or other device (e.g., iPad) and create a Quell Health Account using a de-identified Study Email for the participant. The Study Email will be NCORP19085xxx[xxx=participant ID number]@mail.com.

The coordinator will then train the participant to use the App to start the TENS therapy and to open the App at least 1x per day when their mobile device or tablet is connected to the internet so that their deidentified usage data will be uploaded to the cloud. Participants will be asked not to modify settings in the App other than the intensity on the main screen for the 6 weeks of the study. The usage data (i.e., number of sessions per day, time the device is on the skin, and the intensity of the last session that occurred before connecting the device to the internet) will be downloaded from the Quell Health Account by the TENS device manufacturer and provided to the research team for use in promoting adherence (see **Section 5.3.7 Phone calls**). The participants will be given a daily diary to complete during Weeks 4 (i.e., day 21 - 28) and 6 (i.e., day 35 - 42) in which they will record their daily symptoms and rescue pain medication consumption.

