# 5.3.8 End of Study Visit (Day 42; +/- 5 days) (approximately 1 hour and 15 minutes)

All participants will complete the patient-reported outcome measures, balance tests, conditioned pain modulation test, and lower limb sensation test. The coordinator will also review the list of medications that the participant reported using for CIPN at the beginning of the study and ask the participant if they changed dosages of any of the medications. Any changes will be recorded in the Changes in concomitant analgesic medications form. The coordinator will ask the participant for their device and open the Quell App to ensure final data transfer to the cloud. The data will then be downloaded by the device manufacturer and sent to the Research Base. If the participant does not come to the Week 6 visit, the coordinator will call them up to 3 times to try to reschedule the visit. The rescheduled visit can occur up to 1 month after the date of the 6-week visit. If the participant agrees to come back in, they will be encouraged to keep using the device until the rescheduled visit date.

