## 10.6 Exploratory Analyses.

(1) ANCOVA analysis as in the primary will be used to investigate the effects of TENS on exploratory outcomes (i.e., balance (SPPB balance subscale), descending inhibition (CPM test), physical function (PROMIS short form), CIPN-interference in daily life, CIPN measured by TNAS and CIPN symptom inventory composite measure, depression and anxiety (PROMIS short forms)) at baseline and at Week 6 visits.

(2) Analysis of variance (ANOVA) or an appropriate non-parametric method (e.g., Wilcoxon test) if the normality assumption is not satisfied will be used to evaluate the between arm differences in participant-perceived changes in CIPN symptoms and participant-perceived change in ability to be active.

(3) Descriptive statistics will be used to characterize the distribution of descending inhibition as measured by CPM at baseline. Additionally, the correlation of descending inhibition with CIPN severity (via CIPN20, TNAS, and symptom NRS scores) will be evaluated using a Spearman's correlations.

(4) To explore the predictive effects of baseline descending inhibition on response to TENS, ANCOVA analysis will be used to investigate whether baseline descending inhibition predicts the effect of TENS on CIPN. The model will include CIPN20 at Week 6 as the outcome, baseline CPM test result, treatment group, and baseline CPM test result x treatment group interaction as factors, and study site and the baseline CIPN20 score as covariates.

(5) To explore mechanistic associations between changes in descending inhibition and CIPN symptoms, we will use mediation analysis technique (the method initially formalized by Baron and Kenny, extended to clinical trial settings by Kraemer, and methodologically updated by MacKinnon et al.). Specifically, we will use path modeling to estimate indirect (mediation) effects of changes in the CPM test on CIPN symptoms, and bootstrapping to estimate the 95% confidence intervals. The MPlus software will be utilized.

(6) The proportion of participants who decreased "as-needed" usage of acetaminophen and NSAIDs (defined as taking acetaminophen or NSAIDs, on average, at least 30% fewer days per week in the last week of the trial compared to the baseline week) will be compared by groups using a Chi-Square test.

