(7) The proportion of participants who report, for the impression of change in CIPN symptoms question "very much improved", "much improved", "minimally improved", "no change", "minimally worse", "much worse", and "very much worse") will be compared between treatment groups using a Cochran Armitage Trend Test.

(8) The proportion of participants whose sensation threshold from the monofilament test improved will be reported together with the 95% confidence interval (CI) and tested against the null hypothesis of no improvement.

(9) Descriptive statistics and 95% CIs will be used to assess the percentage of participants and outcome assessors that correctly identify the group to which the participant was assigned as well as the basis for the guesses.

(10)Test, re-test reliability for the CPM test will be evaluated using Intraclass correlation coefficients (ICCs). Test, re-test reliability for the lower limb sensation threshold test will be measured using Kappa statistics.

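### The aim asks for the effect of TENS on lower-limb sensation, but the only efficacy test planned for sensation (10.6, item 8) has no placebo comparison

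*Combined protocol and SAP*

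**What the plan says.** Section 2.4 (Exploratory Aim 1) sets the question: "Investigate the potential effects of TENS on balance, physical function, descending inhibition, lower limb sensation, and anxiety and depression".

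Section 10.6 then assigns analyses. Item (1) states that "ANCOVA analysis as in the primary will be used to investigate the effects of TENS on exploratory outcomes" and gives a closed list that begins "balance (SPPB balance subscale), descending inhibition (CPM test), physical function (PROMIS short form), CIPN-interference in daily life" and goes on to the TNAS, the symptom composite, depression and anxiety. Lower-limb sensation is not on it.

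The monofilament result appears in two items of section 10.6:
- Item (8): the proportion with an improved threshold "will be reported together with the 95% confidence interval (CI) and tested against the null hypothesis of no improvement". No arm or treatment group is mentioned.
- Item (10): test-retest reliability by Kappa.

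The sensation test is done three times: at Screening (5.3.1, "They will complete the CPM test and lower limb sensation test"), at Baseline (5.3.3, "They will complete the PROs, balance tests, CPM test, and lower limb sensation test") and at Week 6 (5.3.8, "balance tests, conditioned pain modulation test, and lower limb sensation test").

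**The concern.** This is a 1:1 placebo-controlled trial with a placebo device built to protect blinding. Item (8) makes no use of that control. It asks whether people improved, whereas the aim asks whether TENS improved them. The outcome comes from the participant saying whether a filament was felt, over sets of 10 trials. Apparent improvement can therefore arise from placebo response, from familiarity with the test, or from chance movement between adjacent filaments.

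Followed as written, the plan yields a p-value for sensation that does not address its own aim, and a small one could be read as support for TENS. The trial exists to inform a phase III design, so a misdirected signal on a candidate outcome has some cost. Primary, secondary, feasibility and safety conclusions are not touched.

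**Working it through.** **1. Match each Aim 1 outcome to its planned analysis.**

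| Aim 1 outcome | Analysis in 10.6 | Compares arms? |
|---|---|---|
| Balance | (1) ANCOVA | Yes |
| Physical function | (1) ANCOVA | Yes |
| Descending inhibition | (1) ANCOVA | Yes |
| Anxiety and depression | (1) ANCOVA | Yes |
| Lower-limb sensation | (8) one proportion against no improvement | No |

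Sensation is the only Aim 1 outcome without a stated between-arm analysis. The wording of (8) is unlikely to be shorthand, because neighbouring items name the comparison when one is meant. Item (2) refers to differences between arms, item (6) says its proportion "will be compared by groups using a Chi-Square test", and item (7) compares treatment groups with a trend test.

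**2. What the item (8) test does when TENS has no effect.**

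The plan gives no figure for this outcome, so there is none to reproduce. Inputs:
- From section 10.3: 126 evaluable participants, so 126/2 = 63 per arm.
- Assumed: two-sided alpha 0.05 (none is stated for this item), and the improvement and worsening rates, which the documents do not give.

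All results are exact calculations. Because the null value is unstated, three readings are shown.

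(a) *Null proportion = 0.* One improver is enough to reject, so P(reject) = 1 − (1 − p)^n. At p = 0.05:
- n = 63: 1 − 0.95^63 = 0.96
- n = 126 (pooled): 1 − 0.95^126 = 0.998

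(b) *Sign test, improved against worsened.* The number of changers is m ~ Bin(n, p_improve + p_worsen). Given m, the number improved is Bin(m, p_improve/(p_improve + p_worsen)), tested against one half and summed over m.

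| Improve / worsen, same in both arms | n = 63 | n = 126 |
|---|---|---|
| 20% / 20% | 3.0% | 3.7% |
| 20% / 15% | 7% | 13% |
| 25% / 15% | 18% | 38% |
| 30% / 15% | 35% | 68% |
| 35% / 15% | 55% | 88% |
| 40% / 15% | 73% | 97% |

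With symmetric noise there is no inflation. Once both arms drift towards improvement, rejection climbs, and pooling makes it climb faster.

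(c) *Null proportion = 0.5.* With n = 63 and 40% improving, rejection in the direction of improvement is 0.00014, and it is smaller at lower rates. The same test rejects in the opposite direction 33% of the time at 40% improved and 99.9% at 20%. That would say only that fewer than half improved.

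**3. What a between-arm comparison does instead.**

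Pearson chi-square, 63 against 63, equal true proportions:

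| True proportion in both arms | 0.20 | 0.25 | 0.30 | 0.35 | 0.40 |
|---|---|---|---|---|---|
| P(reject) | 4.8% | 5.0% | 5.0% | 5.1% | 5.6% |

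It stays close to 5% whatever the common improvement rate. For precision, the 95% CI half-width for the difference is 1.96 × √(2p(1−p)/63), which is 0.105 at p = 0.10 and 0.171 at p = 0.40. With an assumed placebo rate of 10% to 40%, power at two-sided 0.05 is 61% to 81% for a 20-point difference and 20% to 35% for a 10-point difference.

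**The case against.** The strongest reply is that item (8) is silent rather than wrong: it says neither pooled nor within-arm, and an analyst might break it down by arm anyway. Item (9), on blinding guesses, also names no arms. This has some force. The accurate statement is that no between-arm analysis of sensation is *stated*. But a test against no improvement reads naturally as one-sample, and running it in each arm gives two within-arm p-values, not an estimate of the TENS effect.

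Second, the missing details can largely be inferred. Day 0 is called the Baseline Visit, the Screening measurement has an evident use in the Kappa, and improvement most plainly means a move to a weaker filament. That is fair, and these are minor clarifications. The unstated null value is not so easily inferred.

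Third, regression to the mean is a weaker explanation here than usual, because no eligibility criterion uses the filament threshold. Only indirect selection through correlated symptoms could produce it. The argument does not depend on it: placebo response, practice and noise remain.

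Fourth, every rate in the calculations is assumed, a null of exactly zero is an extreme reading, and the sign test is well behaved under symmetric noise. All true. The figures show how far the result depends on unstated choices. They do not estimate this trial's error rate.

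Finally, this is one of ten exploratory items, and a between-arm test would have low power for a small difference. That limits the importance of the point. It does not justify a p-value aimed at a different question.

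**Conclusion.** The concern holds: item (8) is wrongly targeted as written. The core is a matter of logic and needs no assumed rate, because no version of a test against no improvement contrasts active with placebo, and that contrast is what Aim 1 asks for.

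How misleading the result could be depends on the unstated null and on unknown improvement rates. Under the assumptions shown (63 per arm, two-sided 0.05), rejection in favour of improvement with no TENS effect runs from almost never (null of 0.5) to almost always (null of 0).

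The consequence is limited to the conclusion on one exploratory outcome. It should be fixed because the repair is nearly free, not because it threatens the trial.

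**What to change.** Amend section 10.6, item (8):
- Remove the test against no improvement.
- Define improvement as a stated change in filament level from the Baseline visit to Week 6.
- Report the proportion improved in each arm, and the between-arm difference with a 95% CI.
- Compare arms with the chi-square test already used in item (6), or with a site-stratified Cochran-Mantel-Haenszel test, since randomization is stratified by site.

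An ordinal model of the Week 6 threshold, adjusted for baseline threshold and site, would use more of the information but is optional. Given the limited power for small differences, the estimate and its interval should carry the interpretation.

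The cost is a change of analysis wording. Sensation is already measured in all participants at Baseline and Week 6, so no new data, visits or participants are needed.

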#### 10.7 Sensitivity analyses.

(1) Primary and secondary analyses will be repeated in the subset of participants who adhere to the treatment (i.e., adhere to the treatment on  $\geq$  70% of the study days).

#### 10.8 Feasibility analyses.

(1) Descriptive statistics will be used to summarize the following quantitative feasibility outcomes:

- (a) The proportion and 95% CI of screened (i.e., approached) patients who enroll in the study.
- (b) The proportion and 95% CI of randomized participants who adhere to the treatment and complete the primary assessment.
- (c) The proportion and 95% CI of randomized participants who complete the CPM test.
- (d) The proportion and 95% CI of randomized participants who use the device for at least 5 hours / day on at least 70% of the study days.

(2) The participant-reported reasons for low adherence will be summarized by identifying common themes in the qualitative feedback questionnaire.

## 10.9 Evaluation of Toxicity/Adverse Events

Descriptive statistics will be used to summarize AEs in active and placebo device groups. SAEs will be summarized separately as will AEs concluded to be likely related to the treatment.

## 10.10 Interim Analysis

No interim analyses are planned due to the fact that TENS is considered nonsignificant risk by the FDA per the 2006 FDA's "Significant Risk and Nonsignificant Risk Medical Devices" Guidance. [51]

#### **10.11 Ancillary Studies**

Not applicable

## 11. ETHICAL AND REGULATORY CONSIDERATIONS

#### 11.1 Form FDA 1572

Not applicable.

# 11.2 Other Required Documents (IND studies only)

Not applicable.

## 11.3 Institutional Review Board Approval

Prior to initiating the study and receiving study devices, the Investigators at the NCORP will obtain written approval to conduct the study from the NCI Central IRB. Should changes to the study become necessary, protocol amendments will be submitted to the Division of Cancer Prevention (DCP) PIO according to DCP Amendment Guidelines. The DCP-approved amended protocol must be approved by the CIRB prior to implementation of any changes.

## 11.4 Regulatory Approval Process of the Informed Consent Document

Prior to study initiation, the informed consent document will be reviewed and approved by National Cancer Institute (NCI) Division of Cancer Prevention (DCP), and the Central IRB (CIRB). Any subsequent changes to the informed consent must be approved by NCI DCP and CIRB prior to initiation.

### 11.5 Submission of Regulatory Documents

All regulatory documents should be forwarded to the URCC as follows:

URCC\[contact]

### 11.6 Other

This trial will be conducted in compliance with the protocol, Good Clinical Practice (GCP), and the applicable regulatory requirements.

